2.2.3. Utility Measures

- Fluoroscopy time
- Contrast used
- Estimated blood loss during the index procedure
- Thrombectomy time

PROPRIETARY AND CONFIDENTIAL

The information contained in this document is the sole property of Inari Medical

	FLASH STATISTICAL ANALYSIS PLAN	Rev. 3.0 Page 6 of 7
---	--	-------------------------

- Length of intensive care unit stay, if any
- Length of total hospital stay

2.3. Exploratory Analysis

Exploratory analysis will calculate descriptive statistics for baseline demographics, other outcomes of interest, and stratified by subpopulations.

3.0 ANALYSIS POPULATION

3.1. Full Analysis Population

Up to 1000 patients enrolled in the FLASH registry.

3.2. Conservative Therapy Substudy

Up to 300 additional patients with anticoagulation treatment as the initial planned primary treatment strategy for intermediate-risk PE (US patients only).

3.3. Wearables Follow-up Subpopulation

Approximately 100 patients receiving treatment with the FlowTriever System and approximately 100 patients in the Conservative Therapy Substudy, who participated in the Apple Watch substudy (US patients only).

4.0 INCOMPLETE DATE HANDLING AND MISSING DATA

Incomplete dates will follow the following imputation assignment rules:

1. If day is missing but month and year are present, the day will be set to the first date of the month.
2. If both day and month are missing, but year is present, then January 1st will be used as imputed value.
3. If year is missing, then the date is considered missing.

In general, complete case analysis will be used to handle missing values and no other missing data points other than dates will be imputed.

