9 SAFETY ASSESSMENT

9.1 DEFINING ADVERSE EVENTS

An AE is any untoward medical occurrence or exacerbation of an existing medical condition subsequent to treatment with the FlowTriever. AEs are classified in several ways, including severity, relationship, and seriousness.

- Severity (mild, moderate, severe)

- **Mild:** No limitation of usual activities, no therapy or only symptomatic therapy required to treat the injury or illness.
- **Moderate:** Some limitation of usual activities or specific therapy is required.
- **Severe:** Inability to carry out usual activities, hospitalization, emergency treatment, life-threatening events, or mortality.
- Relationships (unrelated, device-related, procedure-related, drug-related, or relationship unknown) are defined below.

Unrelated: The clinical event is completely independent of study procedure/study device and/or evidence exists that the event is definitely related to another etiology.

Device-related: The event is directly related to the study device itself, as defined by its intended use. AEs will be considered unrelated to the device if the complication could have occurred if the device functioned entirely within its specifications.

Procedure-related: Procedure-related events include all AEs that occur at any time of patient participation that was directly related to the procedure. The exception to this rule is an event that is device-related; such events should not also be classified as procedure-related.

Drug-related: Event is attributable to thrombolytic or anticoagulant therapy. These events may occur from inadequate (thrombosis) or excessive therapy (bleeding). A drug-related AE cannot also be classified as device-related, but many will be classified as procedure-related, since the drug may be part and parcel of the index procedure or the event may have occurred within 30 days.

Relationship unknown: The relationship to the study procedure/study device is not known.

A **Serious Adverse Event (SAE)** is an event that meets at least one of the following:

- Is fatal
- Is life-threatening
- Results in persistent or significant disability/incapacity
- Results in permanent impairment of a body function or permanent damage to a body structure
- Results in hospitalization or prolongs a hospitalization
- Necessitates medical or surgical intervention to preclude permanent impairment of a body function or permanent damage to a body structure
- Results in a congenital anomaly or birth defect

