9.2 REPORTING OF EVENTS

The FLASH Registry study was designed to capture real-world data regarding the clinical use of the FlowTriever System (and anticoagulation treatment in the Conservative Therapy Sub-study) and involves the collection of specific information for research and educational purposes only. It does not specify how the FlowTriever System or anticoagulation will be used to treat PE, and decisions regarding a patient's treatment are not influenced by the study. This is a data collection study only; there is nothing investigational or experimental in the patient's medical treatment.

Therefore, the study will only capture AEs related to the patient's PE condition and its treatment. Reportable AEs include all events considered in the safety analyses (e.g., major bleeding^c), all device- and/or procedure-related AEs, as well as any event resulting in mortality.

The AEs will be captured on the Adverse Event CRF and should include, wherever possible, severity, duration, outcome, the Investigator's description of the event, and his/her medical judgment as to the relationship of the AE (i.e., not related, related, or relationship unknown) to the study device, to the index procedure or any subsequent procedure(s), to a thrombolytic agent or anticoagulant, or underlying disease.

- Non-serious reportable AEs are to be submitted via the electronic data capture system (EDC) in a timely fashion.
- Reportable SAEs must be reported to the Sponsor within 5 business days of the Investigator's knowledge of the event. The event is reported in the EDC.

Appendix 1 includes a list of possible SAEs associated with thrombectomy, including those events considered major device-related events and major morbidity. These events are considered reportable at all time points throughout the study and require submission to the Sponsor and the IRB/EC and regulatory authorities, as required.

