12.2 SITE MONITORING VISITS

Interim monitoring visits may be conducted by the Sponsor or designee in-person or remotely to ensure compliance with the protocol, and other written instructions and regulatory guidelines according to a study-specific monitoring plan.

The main responsibilities of the Monitor or designee are to ensure adherence to the protocol; to verify all data are correctly and completely recorded and reported; confirm that informed consent is obtained and recorded for each patient before any medical record or personal health information is shared with any study representatives. The Investigator and assisting staff must agree to cooperate with the Monitor or Sponsor representative to resolve any study-related action items, errors, or possible misunderstandings concerning the findings detected during these monitoring visits or data review.

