13.4 INDEPENDENT MEDICAL MONITOR

An independent Medical Monitor, an independent physician who is not a participant in the study, will review AEs that occur throughout the course of the study. The activities of the Medical Monitor will be guided by the Safety Manual. The Medical Monitor will be responsible for classifying events by severity, relationship, and seriousness, as well as whether they meet MAE criteria related to the primary safety endpoint. For the Primary Endpoint, the Medical Monitor AE assessments will supersede those of the Investigators when there are differences.

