2.0 STUDY DESIGN

The FLASH Registry is a prospective, single-arm, multicenter study of the FlowTriever System for intermediate-risk (submissive) and high-risk (massive) PE. The Registry will collect data on demographics and comorbidities; details from the PE diagnosis and treatment; and clinical outcomes through six months follow-up. Up to 1000 patients (up to 800 in the US and up to 200 in Europe and UK) with PE will be enrolled at up to 100 Registry sites (up to 70 in the US, up to 30 in Europe and UK).

A Conservative Therapy Substudy, with up to 300 additional patients with anticoagulation treatment as the initial planned primary treatment strategy for intermediate-risk PE, will be evaluated in the US only. The Conservative Therapy Substudy will collect data on demographics and comorbidities; details from the PE diagnosis and treatment; and clinical outcomes through six months of follow-up.

All patients will have follow-up evaluations after the index procedure (Full Analysis Population), or after primary treatment of anticoagulation is administered at baseline (Conservative Therapy Substudy), at 48 hours (+ 36 hours), 30 days(+ 15 days), and six months (+ 90 days).

In addition to the follow-up schedule, approximately 100 patients receiving treatment with the FlowTriever System and approximately 100 patients receiving anticoagulation treatment as their primary treatment for PE will be asked to participate in ongoing data collection for 6 months utilizing an Apple Watch (for US only patients). Patients will be provided with a pre-configured Apple Watch with cellular capabilities at the 48 hour visit. Patients will be expected to wear the Apple Watch daily, with data collection occurring through their 6 month visit.

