2.2.1. Secondary Safety Endpoints

- Individual components of the MAE composite endpoint
 - Device-related death through 48 hours after the index procedure
 - Major bleeding through 48 hours after the index procedure, summarized by commonly used scales and each individual element of each scale
 - Clinical deterioration defined by hemodynamic or respiratory worsening
 - Device-related pulmonary vascular injury
 - Device-related cardiac injury
- Major access site complications requiring open surgical or endovascular intervention or blood transfusion
- All-cause mortality within 30 days
- Device-related serious AEs within 30 days

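### SAP 4.0 moves every partial date backward, so a death or device-related SAE after day 30 with an incomplete date can be counted as a 30-day event (minor)

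*SAP*

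**What the plan says.** SAP 4.0 gives two rules that assign a date. The first is "If day is missing but month and year are present, the day will be set to the first date of the month". The second is "If both day and month are missing, but year is present, then January 1st will be used as imputed value". A date with no year is treated as missing. The rules cover incomplete dates of every kind. Section 4.0 has no exception for deaths or adverse events, no lower limit at the start of treatment or the last date known alive, and no sensitivity analysis. The protocol has no rule that overrides it.

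Two secondary safety endpoints in SAP 2.2.1 depend on a day-30 cut: "All-cause mortality within 30 days", and device-related serious AEs over the same period. SAP 5.2 assesses the endpoints in both the Full Analysis Population and the Conservative Therapy Substudy. For the substudy, SAP 2.0 counts follow-up visits from anticoagulation ("or after primary treatment of anticoagulation is administered at baseline (Conservative Therapy Substudy").

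Protocol 7.5 runs follow-up to 6 months (± 90 days), and Protocol 9.2 makes any event resulting in mortality reportable. Deaths after day 30 will therefore be in the database.

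**The concern.** A rule that always picks the earliest possible date suits a medical-history item. For an event that must be placed before or after day 30, it can only push the event toward the window. With only the day missing, the misplaced death lands on an ordinary-looking day after treatment, so a check for impossible dates would not find it.

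A separate defect comes from having no lower limit. Protocol 9.1 defines an AE as "any untoward medical occurrence or exacerbation of an existing medical condition subsequent to treatment with the FlowTriever". Yet an AE in the procedure month with its day missing is dated before the procedure, unless the procedure fell on the 1st. Whether that loses events depends on how the count is programmed, which the SAP does not say.

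At stake are 30-day all-cause mortality in both cohorts and, in FlowTriever patients, 30-day device-related SAEs. The study is descriptive, so these counts are themselves the result.

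**Working it through.** The plan gives no figure to reproduce. The check applies the SAP 4.0 rules to the calendar.

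**Assumptions.** Procedure and event dates are spread evenly over a 365-day year. All shares are conditional on the date being partial. The documents give neither the number of partial dates nor deaths by day.

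**Worked example.** Procedure 10 March, death 25 April: 21 days to 31 March plus 25 = day 46. With the day missing, the date becomes 1 April: 21 + 1 = day 22.

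**Day missing, true day 31 or later.** Let k be the true day and m the day of the month.
- Imputed day = k − (m − 1). The shift is 0 to 30 days, always backward.
- The event crosses to day 30 or earlier when m − 1 ≥ k − 30.
- For k = 31 to 60 the threshold k − 30 runs from 1 to 30, so the crossing probabilities sum to the mean of (m − 1).
- Mean of (m − 1): a 31-day month contributes 465, a 30-day month 435, February 378. (7 × 465 + 4 × 435 + 378) / 365 = 5373 / 365 = 14.72.
- Average share over the 30 days: 14.72 / 30 = **49.1%**. Enumerating all 730 procedure dates in two illustrative years (2021–2022) gives the same figure, with 73.7% for days 31–45 and 24.4% for days 46–60.
- From k = 61, crossing would need m ≥ 32, so the share is **0%**.
- About 1 / 0.491 = 2.04 deaths on days 31–60 with a missing day produce one misplaced death.

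**Day missing, true day 0 to 30.**
- The imputed day is never later than the true day, so no event moves past day 30.
- The imputed day is negative when m − 1 > k. Summed over k = 0 to 30 this is again 14.72, and 14.72 / 31 = 47.5%. These events stay in a count of day 30 or earlier and drop out only if the count requires day 0 or later.

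**Would a floor at the procedure date cure the late-death error?** No. For k ≥ 31 the imputed day is at least 31 − 30 = 1, so a floor at day 0 never takes effect and the 49.1% is unchanged. A last-known-alive date helps only if it is day 31 or later.

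**Day and month missing.** Let y be the day of the year.
- Imputed day = k − (y − 1), so deaths well after day 60 can cross. Example: procedure 15 December 2020, death 20 May 2021 (day 156), imputed 1 January 2021 = day 17.
- The share at day 30 or earlier is 1 − (k − 30)/365. For days 61–180 the mean of k − 30 is 90.5, giving 1 − 90.5/365 = 75.2%. Most of these (66.7%) are dated before the procedure, and 8.5% (31/365) fall on days 0–30.

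**Effect per misplaced death.** 1/1000 = 0.1 percentage points in the main registry; 1/300 = 0.33 in the substudy.

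**The case against.** The strongest reply is that this will rarely arise. It needs a death soon after day 30, a known month but a lost day, and a query that was never resolved. Deaths are reportable, and "Reportable SAEs must be reported to the Sponsor within 5 business days" of the investigator learning of them. Monitors are there "to verify all data are correctly and completely recorded and reported", and Protocol 12.4.1 obliges sites to answer data queries. If every death and SAE date is complete, the effect is zero. This stands, and it is why the point is minor.

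It is also true that, under a count of day 30 or earlier, the rule loses no true 30-day event and can only overcount, which is cautious for the device. It is not cautious for the substudy, where the same overcount overstates mortality on anticoagulation.

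Four stronger readings are tempting, and the documents do not support them:
- *The missing floor causes the late-death error.* It does not. The backward direction does, and a floor leaves the 49.1% unchanged.
- *The primary endpoint is biased.* Under Protocol 13.4 the Medical Monitor classifies events, "as well as whether they meet MAE criteria related to the primary safety endpoint", and that assessment prevails over the investigator's for the primary endpoint. Protocol 13.4 does not assign the day-30 cut to the monitor.
- *About half of deaths in the second month will be misplaced.* The 49% applies only to deaths with a missing day, under an even spread of dates.
- *A comparison of the cohorts is distorted.* The rule is the same in both, SAP 5.2 names only tests for paired outcomes, and nothing shows that partial dates would be more frequent in one cohort.

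**Conclusion.** The concern holds as a minor point. Followed as written, SAP 4.0 can place a death or device-related SAE from after day 30 inside the 30-day window. No other text in either document corrects this. With only the day missing, exposure is limited to days 31–60; with the month also missing it extends further, though that case is more remote. Impossible pre-procedure dates are a second, separate consequence, and they cost events only if the count requires day 0 or later.

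The size rests on a number that the documents do not give, the count of partial death and SAE dates, which is probably small. The shares describe the calendar under even spread; they are not expected rates in the registry. The identified effect is on two secondary counts, at 0.1 or 0.33 percentage points per misplaced death at the full cohort sizes. Lengths of ICU and hospital stay might also be derived from dates, but the documents do not say how, so the point is not extended to them.

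**What to change.** Add to SAP 4.0, for partial dates of deaths and SAEs:

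1. Bound the possible date range below by the start of treatment (index procedure, or start of anticoagulation in the substudy) and, for deaths, by the last date known alive. Bound it above by the earliest report or site-awareness date.
2. Classify the event by day 30 whenever the bounded range settles it. In the worked example, a death known only as April spans day 22 to day 51 (21 + 30). If the patient was known alive on 12 April (day 33), it is outside; if it was reported by 8 April (day 29), it is inside.
3. If the range still straddles day 30, keep the event in the main count and report the two 30-day counts with and without it.
4. Keep the current rule for medical-history dates.

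The upper bound matters. Using calendar months alone, 47.5% of true day 0–30 events with a missing day would straddle day 30 (the mean number of days left in the month is also 14.72, and 14.72 / 31 = 47.5%), so the figure without them would understate safety events.

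The cost is a few sentences and slightly more programming. If a straddling event remains, the report shows a small range instead of one figure; if none does, each count stays a single figure.

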5.0 STATISTICAL METHODS AND ANALYSIS

5.1. Sample Size

The sample size of up to 1000 patients reflects an adequate size to accrue data on the real-world use of FlowTriever System for PE, as assessed in up to 100 Registry sites (up to 70 in the US, up to 30 in Europe and UK).

PROPRIETARY AND CONFIDENTIAL

The information contained in this document is the sole property of Inari Medical

	FLASH STATISTICAL ANALYSIS PLAN	Rev. 3.0 Page 7 of 7
---	--	-------------------------

5.2. Primary, Secondary, and Exploratory Endpoint Analysis

This is an observational study and as such is not hypothesis-driven. The endpoints will be assessed for patients in the Full Analysis Population, and Conservative Therapy Substudy, with descriptive statistics. Continuous variables will report any combination of mean, median, Q1, Q3, IQR, minimum and maximum, while the categorical variables will report frequency count and percentages (%). Crude p-values may be reported for descriptive statistics; paired continuous outcomes will use Wilcoxon Signed-Rank Test while paired categorical outcomes will use McNemar's Test.

6.0 DOCUMENT VERSION HISTORY

REV	DESCRIPTION OF CHANGE
1.0	New Release
2.0	Updated to include Conservative Therapy and Apple Watch
3.0	Updated to be in alignment with CIP version 8.0

PROPRIETARY AND CONFIDENTIAL

The information contained in this document is the sole property of Inari Medical
